5.2. General Considerations

Statistical analysis of this study will be the responsibility of Lilly or its designee. Any change to the data analysis methods described in the protocol will require an amendment ONLY if it changes a principal feature of the protocol. Any other change to the data analysis methods described in the protocol, and the justification for making the change, will be described in the SAP or the CSR. Additional exploratory analyses of the data may be conducted as deemed appropriate.

All analyses will be conducted under the guidance and approval of Lilly statisticians.

The treatment groups mentioned in this document are dulaglutide (Dula) 1.5 mg and 0.75 mg (pooled); Dula 1.5 mg; Dula 0.75 mg; and Placebo during the double blinded period (randomization to Week 26) unless otherwise specified. Placebo becomes Placebo/Dula 0.75 mg during the open label period (Week 26 to Week 52) while the other treatment groups are unchanged.

For the purposes of tables, figures, and listings (TFLs), up to Week 26 the treatment groups will be All Dula (pooled dulaglutide doses); Dula 1.5; Dula 0.75; and Placebo. Placebo will be the reference treatment across all statistical reports whenever the treatment effect is compared between All Dula and Placebo, Dula 1.5 and Placebo, and Dula 0.75 and Placebo.

Up to Week 52 or to Week 56 (for selected safety parameters such as ADA at safety follow-up (Visit 801 [V801])), treatment will be expressed in the TFLs as All Dula, Dula 1.5, Dula 0.75, and Placebo/Dula 0.75 representing (Dula 0.75/0.75, Dula 1.5/1.5 pooled), Dula 1.5/1.5, Dula 0.75/0.75, and Placebo/Dula 0.75, respectively. No inference will be made among the treatment groups after Week 26 to Week 52 or from Week 26 to V801. Within-treatment comparisons

between different scheduled visits such as Week 26 and Week 52 for parameters such as HbA1c change (and others) from baseline may be performed.

Generally, V801 data will not be summarized unless otherwise stated, but V801 data may be listed.

Efficacy and safety data will be summarized by each treatment group at each scheduled visit unless otherwise stated.

Six patient populations are defined for the analyses in this study with detailed information listed in [Table GBGC.5.1](#).

Unless otherwise specified, data listings will consist of all randomized patients. Both efficacy and safety analyses will be conducted using the ITT population. For safety except hypoglycemia analyses, all measurements including those made after taking rescue therapy will be included. Hypoglycemia analyses will be evaluated in the ITT population after censoring the data following administration of any rescue medication.

Unless otherwise specified, all tests of treatment effects will be conducted at a 2-sided alpha level of 0.05 and confidence intervals (CI) will be calculated at 95%, 2 sided.

For subgroup analyses, all tests of interactions between treatment and factors of interest will be conducted at a 2-sided alpha level of 0.10.

Visit 2 is the baseline visit. Baseline measurement for a corresponding parameter of interest is defined as the last nonmissing value taken prior to the first dosing of study drug. Baseline HbA1c value will be used to define HbA1c strata for analyses.

Unless otherwise specified, longitudinal continuous measures will be analyzed using MMRM with stratification factors (insulin usage [yes, no], metformin usage [yes, no], HbA1c strata [HbA1c: <8.0%, $\geq 8.0\%$]), treatment (Dula 1.5, Dula 0.75, Placebo or Placebo/Dula 0.75), visit, and treatment-by-visit as fixed effects, and corresponding baseline measurement as a covariate unless otherwise noted. The Kenward-Roger method will be used to estimate denominator degrees of freedom, and the REML approach to obtain model estimate. An unstructured covariance structure will be used to model the within-patient errors. If this model fails to converge, the following covariance structures will be tested in order:

- Toeplitz with heterogeneity
- Autoregressive with heterogeneity, by visit
- Compound symmetry with heterogeneous variances, by visit
- Toeplitz
- Autoregressive
- Compound symmetry without heterogeneous variances, by visit

The first variance-covariance structure that converges will be used.

For continuous variables, summary statistics will include the number of patients, mean, SD, median, minimum, and maximum for both the actual and change from baseline for each treatment group at each visit. If a patient has no postbaseline data, the patient will be excluded from inferential statistical analysis. For data collected prior to first dosing, or randomization date if the first dosing date is not available, an analysis of variance (ANOVA) model with treatment (Dula 0.75, Dula 1.5, and Placebo) will be fitted. For post-first dosing longitudinal data, the aforementioned MMRM model will be fitted. For nonlongitudinal endpoint data, an ANCOVA model will be fitted by removing visit and visit-by-treatment interaction terms from its corresponding aforementioned MMRM model. Least-squares mean (LSmean) and standard errors derived from the corresponding statistical model will also be displayed for the change from baseline at each visit for each treatment group. Treatment comparisons at the same visit will be displayed showing the LSmean and the 95% CIs for the treatment differences (All Dula – Placebo; Dula 1.5 – Placebo; Dula 0.75 – Placebo) at the same visit along with the corresponding p-values up to Week 26. Appropriate estimate statements will be constructed in each aforesaid model (ANOVA, MMRM, or ANCOVA) to obtain a corresponding endpoint estimate for All Dula and the treatment comparison between All Dula and placebo at each visit of interest up to Week 26.

Unless otherwise stated, categorical variables will be summarized by sample size, frequency, and percentages for each treatment group at each visit. Fisher's exact test will be used to compare the difference among the 3 treatment groups and between All Dula and placebo.

For LOCF, the last nonmissing value will be imputed as the endpoint if the endpoint is missing. Any missing component of date and/or time may be imputed following Lilly standards.

Additional analyses may be performed even after datalock if deemed needed.

All statistical analyses will be conducted with R or SAS Version 9.4® or higher unless otherwise stated.

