8.3.3. Patient Discontinuation from the Study

Patients will be discontinued from the study under the following circumstances:

- Patient Decision
 - The patient (and/or parent or legal guardian) withdraws his/her/their consent
- Lost to Follow-Up
 - A patient will be considered lost to follow-up if he/she repeatedly fails to return for scheduled visits and is unable to be contacted by the study site.
 - Site personnel are expected to make diligent, repeated attempts to contact patients who fail to return for a scheduled visit or who were, otherwise, unable to be followed up by the site. Site personnel, or an independent third party, may attempt to collect the vital status of the patient within legal and ethical boundaries for all patients randomized, including those who did not get study drug.
- Inadvertent Enrollment
 - Patients found to have T1DM, a hemoglobinopathy or other disorder that interferes with the accurate determination of the primary endpoint, or are pregnant or breastfeeding at the time of enrollment, will be discontinued.
- Pregnancy and Breastfeeding
 - Patients found to be pregnant or breastfeeding during the trial will be discontinued.

Patients who discontinue the study early will have end-of-study procedures performed as shown in the Study Schedule ([Attachment 1](#)) and will also have a follow-up safety visit 30 days after study discontinuation (Visit 801).

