10.4.1.1. Serious Adverse Events

Serious adverse event collection begins after the patient and parent or legal guardian have signed informed consent and assent, respectively, and the patient has received study drug. If a patient experiences an SAE after signing informed consent, but prior to receiving study drug, the event will NOT be reported as serious unless the investigator feels the event may have been caused by a protocol procedure.

Planned surgeries should not be reported as SAEs unless the underlying medical condition has worsened during the course of the study.

Study site personnel must alert Lilly or its designee of any SAE within 24 hours of investigator awareness of the event via a Lilly-approved method. If alerts are issued via telephone, they are to be immediately followed with official notification on study-specific SAE forms. This 24-hour notification requirement refers to the initial SAE information and all follow-up SAE information.

An SAE is any AE from this study that results in 1 of the following outcomes:

- Death
- Initial or prolonged inpatient hospitalization
- A life-threatening experience (i.e., immediate risk of dying)
- Persistent or significant disability/incapacity
- Congenital anomaly/birth defect
- Considered significant by the investigator for any other reason.

Important medical events that may not result in death, be life-threatening, or require hospitalization may be considered serious adverse drug events when, based on appropriate medical judgment, they may jeopardize the patient and may require medical or surgical intervention to prevent 1 of the outcomes listed in this definition.

When a condition related to the drug delivery system (i.e., the SDP) necessitates medical or surgical intervention to preclude either permanent impairment of a body function or permanent damage to a body structure, the serious outcome of "required intervention" will be assigned.

Serious adverse events occurring up to and including the patient's last study visit will be collected, regardless of the investigator's opinion of causation, in the clinical data collection database and the pharmacovigilance system at the sponsor.

The investigator does not need to actively monitor patients for AEs once the trial has ended, unless provided otherwise in the protocol. However, if an investigator becomes aware of SAEs occurring to a patient after the patient's participation in the trial has ended, the investigator

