5.15.1. Adverse Events

An AE will be coded using the Medical Dictionary for Regulatory Activities (MedDRA). Unless otherwise specified, AEs will be reported using the MedDRA system organ class (SOC) and preferred term (PT).

Summary statistics will be provided for the following: medical history including preexisting conditions, deaths, AEs, TEAEs, SAEs, AESIs, and study discontinuations due to death or AEs from baseline to Week 26 and from baseline to Week 52. The number of patients and proportions of patients experiencing the AEs will be reported for each treatment group, and Fisher's exact tests will be used to compare the treatment groups.

Treatment-emergent AEs are defined as events that are newly reported after the first dosing or reported to worsen in severity from the first dosing. If the first dosing date is missing, the randomized date will be used to impute the first dosing date for TEAE determination. The incidence of patients with at least 1 TEAE will be reported, and the proportion of patients experiencing each reported TEAE will be presented by PT, SOC, and treatment group. The proportion of patients experiencing each reported TEAE that are assessed as possibly related to the study treatment will also be summarized (see details in Section 5.2). Additionally, a summary of TEAEs by maximum severity will be presented descriptively by treatment group.

A listing of patients discontinuing the study due to AE or death will be generated.

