5.15.2.2. Pancreatitis

The incidence of acute or chronic pancreatitis will be summarized descriptively for each treatment group separately for investigator-reported and adjudicated events from baseline to Week 26, from baseline to Week 52. The individual patients with this event will be listed along with lab tests, including lipase, amylase, and p-amylase.

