5.15.2.3. Thyroid C-Cell Hyperplasia and C-Cell Neoplasms

The incidence of all types of thyroid tumors/neoplasms (benign and malignant) including C-cell hyperplasia will be summarized by each treatment group from baseline to Week 26, baseline to Week 52. The incidence of TEAEs associated with all types of thyroid tumors/neoplasms including C-cell hyperplasia will be reported for each treatment group from baseline to Week 26, baseline to V801. The individual patients with this event will be listed along with the laboratory tests, including calcitonin.

For calcitonin, summaries and analysis for changes from baseline and treatment emergent abnormal values will be provided as well as listing of abnormal values.

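### Deaths, SAEs, TEAEs and most AEs of interest arising in the 30-day safety follow-up enter no committed incidence table, so the whole-study safety summary is incomplete

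*SAP*

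**What the plan says.** The SAP's default for the safety follow-up visit is in section 5.2: "Generally, V801 data will not be summarized unless otherwise stated, but V801 data may be listed". The same section allows some output to run later, "Up to Week 52 or to Week 56 (for selected safety parameters such as ADA at safety follow-up", and names only anti-drug antibodies (ADA) as an example.

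The event sections then set their own windows:

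- 5.15.1 covers "deaths, AEs, TEAEs, SAEs, AESIs, and study discontinuations due to death or AEs from baseline to Week 26 and from baseline to Week 52".
- 5.15.2.2 covers investigator-reported pancreatitis and "adjudicated events from baseline to Week 26, from baseline to Week 52".
- 5.15.2.5 (allergic, hypersensitivity and injection site reactions), 5.15.2.6 (renal impairment) and 5.15.4 (malignant events) use the same two windows.
- 5.15.2.3 is the exception. TEAEs associated with thyroid neoplasms "will be reported for each treatment group from baseline to Week 26, baseline to V801".

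On collection, Protocol 10.4.1.1 begins "Serious adverse events occurring up to and including the" and goes on to the patient's last study visit, regardless of causation. Protocol 7.1 and the Study Schedule footnotes require AE information at Visit 801. Under Protocol 8.3.3, patients who leave the study early "will also have a follow-up safety visit 30 days after study discontinuation (Visit 801").

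**The concern.** The follow-up is one of the four study periods in Protocol 7.1, and final database lock waits for it (Protocol 12.2.11). Its main safety yield is AEs and SAEs. Under the SAP's default, a death, SAE, pancreatitis case or hypersensitivity reaction with onset after Week 52 is collected and locked but appears in no planned incidence table.

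The SAP is also uneven. Pancreatic, thyroid and immune-related safety stand side by side in the secondary safety objectives (SAP 4.2), yet only thyroid TEAEs are carried to Visit 801. A reader of the study report who wanted the number of patients with an SAE at any time on study could not get it from the planned tables.

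**Working it through.** The plan gives no figure for this point, so the check sets the windows side by side and then scales the uncounted time.

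**Windows**

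| Event class | SAP section | Last summary window | Visit 801 exception stated? |
|---|---|---|---|
| Deaths, AEs, TEAEs, SAEs, AEs of special interest | 5.15.1 | Week 52 | No |
| Pancreatitis | 5.15.2.2 | Week 52 | No |
| Thyroid-neoplasm TEAEs | 5.15.2.3 | Visit 801 | Yes |
| Allergic, hypersensitivity, injection site | 5.15.2.5 | Week 52 | No |
| Renal impairment | 5.15.2.6 | Week 52 | No |
| ADA | 5.15.3 | Week 52 | No, although 5.2 names ADA as a Week 56 parameter |
| Malignant events | 5.15.4 | Week 52 | No |

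The 5.2 default applies unless a section says otherwise, and only the thyroid section does. SAP 5.15.1 starts the TEAE definition at first dose and gives no end. An event in the follow-up therefore qualifies as a TEAE but falls outside every TEAE summary.

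**Listings.** Protocol 12.2.9.2 commits to listing all AEs and TEAEs by patient and visit. SAP 5.2 makes listing of Visit 801 data optional, and SAP 5.15.1 itself commits only to a listing of patients who discontinue because of an AE or death. The two documents differ in strength here.

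**Uncounted time.** Inputs are 52 weeks of treatment and about 30 days of follow-up (Protocol 7.1), and 150 enrolled with 120 completers (SAP 5.1).

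- Treatment days: 52 × 7 = 364.
- Share per completer: 30 / (364 + 30) = 30/394 = 7.6%. If follow-up is taken as 4 weeks: 28/392 = 7.1%.
- Total if 120 patients contribute follow-up: 120 × 30/365 = 9.9 patient-years.
- Total if all 150 do: 150 × 30/365 = 12.3 patient-years.

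The 120 is the planned number of 26-week completers. Using it as the number who reach Visit 801 is an assumption.

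**Early leavers.** Take a patient who leaves the study at Week 10. Visit 801 falls at about day 70 + 30 = 100, a little after Week 14. An event two weeks after exit has its onset at Week 12. If windows are cut by onset date, it counts in baseline to Week 26. If they are cut by visit, it is Visit 801 data and does not count. The SAP does not say which cut applies. At the planned 20% dropout about 0.20 × 150 = 30 patients could be affected. If the 10% missing Week 26 HbA1c assumed in the 2019 update (SAP 5.1) approximates dropout, the number is about 0.10 × 150 = 15. Both are upper figures, because patients lost to follow-up or withdrawing consent may not attend Visit 801.

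**The case against.** The strongest reply is that the SAP follows the protocol. Protocol 12.2.9.2 confines the summaries of TEAEs, SAEs and discontinuations due to AEs or death to the treatment period. The secondary safety objectives are set at Week 26 and Week 52, and the SAP windows match them. Dulaglutide stops at Week 52 and background diabetes medication is then adjusted, so keeping the off-drug weeks apart is defensible. In a trial of about 150 patients, listings would show each late case. All of this stands, and it rules out calling the omission a protocol breach or saying that the events are lost.

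A reader might go further and infer three things that the documents do not support:

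- **That the Week 26 or Week 52 rates are understated.** A proportion over a defined window is not too low because later days lie outside it. The 7.6% is a share of observation time, not of events.
- **That the double-blind comparison is biased towards the arm with more withdrawals.** This needs events to be cut by visit. The SAP never says so, and an onset-date cut would count those events. The 5.2 sentence stands next to text about summaries by scheduled visit and may have been meant only for by-visit data.
- **That early leavers are the patients most likely to have late events.** Nothing in the documents shows it. Patients who permanently stop study drug generally stay in the study and attend all visits (Protocol 8.3.2, and 10.4.1.2.4 and 10.4.1.2.6 for allergic reactions and renal impairment). Exits from the study under 8.3.3 are for withdrawn consent, loss to follow-up, inadvertent enrollment, and pregnancy or breastfeeding.

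The reply does not explain why thyroid TEAEs are carried to Visit 801 and the other AEs of interest are not, or why the Visit 801 listing is optional in the SAP.

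**Conclusion.** The point holds as an incomplete whole-study safety summary. Deaths, SAEs, TEAEs, pancreatitis, hypersensitivity, renal and malignant events with onset in the follow-up enter no committed incidence table, while thyroid-neoplasm TEAEs do. The uncounted time is about 30 of 394 days per completer, or 9.9 to 12.3 patient-years if 120 to 150 patients contribute follow-up. The number of events in that time cannot be derived from the documents. No bias in the Week 26 or Week 52 rates has been shown. For early leavers the SAP is silent on the cut-off rule, and this should be settled in the text before the tables are programmed. The ADA window in 5.15.3 also disagrees with 5.2.

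**What to change.** Keep the existing Week 26 and Week 52 tables and make these changes to the SAP:

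1. In 5.2, exempt safety events from the Visit 801 exclusion.
2. In 5.15.1, 5.15.2.2, 5.15.2.5, 5.15.2.6 and 5.15.4, add a baseline-to-Visit-801 summary of deaths, SAEs, TEAEs and AEs of interest by treatment sequence. It should be descriptive only, in line with the rule of no inference after Week 26, and follow the pattern of 5.15.2.3.
3. State that AEs are assigned to the Week 26 and Week 52 windows by onset date, so that follow-up events before Week 26 in early leavers are counted in the double-blind summary.
4. Make the listing of Visit 801 AEs mandatory, to match Protocol 12.2.9.2.
5. Reconcile the ADA window in 5.15.3 with 5.2.

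The cost is SAP wording and a few extra table runs on data already collected. Whole-study event counts may come out slightly higher and will include an off-drug period, so the new tables should be labelled accordingly.

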5.3. Graphical Approach to Adjust Multiplicity

To control overall Type 1 error, a graphical approach (Bretz et al. 2011) presented in [Figure GBGC.5.2](#) will be used to compare the treatment effect among the pre-defined parameters of interest to address the selected key secondary objectives defined in the protocol at Week 26 for the ITT population only once the primary objective (H1) is achieved. In this figure, the numbers along the arrows represent the fraction of alpha from a null hypothesis, if it is rejected, to be passed to the next hypothesis. This graphical approach will be conducted separately for each of the following estimands, and each will be tested at the full significance level of 0.05:

- Treatment regimen estimand from the ITT population regardless of rescue status or treatment adherence coupled with the washout approach for multiple imputation.
- Efficacy estimand from the ITT population with censoring of the postrescue data.
- Efficacy estimand from the ITT population with censoring of the postrescue data and excluding lifestyle only/metformin naïve patients.

Figure GBGC.5.2 may be revised per the observed correlation matrix using blinded data among the parameters of interest at Week 26 prior to datalock.

[figure not shown]

Figure GBGC.5.2. Graphical testing scheme for Study H9X-MC-GBGC.

- H_1 : Superiority test of dulaglutide pooled arm (Pooled dulaglutide 1.5 mg and 0.75 mg) versus placebo in mean change from baseline in HbA1c at 26 weeks
- H_2 : Superiority test of dulaglutide 1.5 mg versus placebo in mean change from baseline in HbA1c at 26 weeks
- H_3 : Superiority test of dulaglutide 0.75 mg versus placebo in mean change from baseline in HbA1c at 26 weeks
- H_4 : Superiority test of dulaglutide pooled arm versus placebo in proportion of patients achieving an HbA1c $<7.0\%$ at 26 weeks
- H_5 : Superiority test of dulaglutide 1.5 mg versus placebo in proportion of patients achieving an HbA1c $<7.0\%$ at 26 weeks
- H_6 : Superiority test of dulaglutide 0.75 mg versus placebo in proportion of patients achieving an HbA1c $<7.0\%$ at 26 weeks
- H_7 : Superiority test of dulaglutide pooled arm versus placebo in mean change from baseline in FBG at 26 weeks
- H_8 : Superiority test of dulaglutide 1.5 mg versus placebo in mean change from baseline in FBG at 26 weeks
- H_9 : Superiority test of dulaglutide 0.75 mg versus placebo in mean change from baseline in FBG at 26 weeks
- H_{10} : Superiority test of dulaglutide pooled arm versus placebo in mean change from baseline in BMI at 26 weeks
- H_{11} : Superiority test of dulaglutide 1.5 mg versus placebo in mean change from baseline in BMI at 26 weeks

- H_{12} : Superiority test of dulaglutide 0.75 mg versus placebo in mean change from baseline in BMI at 26 weeks

